### **Benefits**

Participating in this study may allow patients to receive specialised Toric IOLs which are not routinely given in NHS cataract surgery. As a result of the additional study visit, the participants will also have additional care and screening for both vision and mobility. The extra study visit after the surgery provides additional

Vision and balance changes after bilateral implantation of Toric IOLs  
IRAS ID: 286913

follow up opportunity and if the investigators of this study find that you have a rotated lens, then they will be able to advise on whether additional treatment would be beneficial for the patients.

This is a new study to explore the benefit of full vision correction during cataract surgery on vision characteristic and dynamic balance in functional activities for fall risk management. The study can improve the understanding of visual impact on functional biomechanics and will provide evidence to inform fall risk management from vision perspective. Fall risk improvement is not currently a considering factor for IOLs selection in Cataract management, but this study may provide the needed evidence for better vision and fall management among elderly.

### 3. OBJECTIVES AND OUTCOME MEASURES/ENDPOINTS

#### 3.1 Primary objective

The objective of the study is to compare the effects of Toric intraocular lens versus Monofocal intraocular lens replacement on dynamic stability among cataract patients with astigmatism using a randomised controlled trial.

It is hypothesized that Toric intraocular lens will have additional correction of astigmatism after the cataract surgery resulting in and better outcomes in dynamic stability and higher chance of “spectacle-free”.

There are two arms of the trial: Monofocal Toric intraocular lens versus Monofocal non-Toric intraocular lens

The research question is based on the PICOT criteria:

P Population	Cataract patient with astigmatism >1.0DD awaiting intraocular lens replacement surgery
I Intervention	Monofocal Toric intraocular lens
C Comparison group	Monofocal non-Toric intraocular lens
O Outcome of interest	Primary- Dynamic stability will be measured by motion sensor during functional movements (crossing obstacles, turning and stair walking)  Secondary- Eye tracking characteristics, visual function, risk of fall, vision specific quality of life questionnaire and Toric IOL rotation.
T Time	Before operation (T1) and 3-6 months after each eye operation (T2, T3)

Vision and balance changes after bilateral implantation of Toric IOLs  
IRAS ID: 286913

### **3.2 Secondary objectives**

The second objective is to compare the effect of Toric versus Non-Toric monofocal intraocular lenses implantation on eye tracking characteristics, visual function, intraocular lens orientation, risk of falls and vision related quality of life.

### **3.3 Outcome measures/endpoints**

#### **Sample size:**

140 participants will be recruited from patients undergoing cataract surgery at the Royal Eye Infirmary of the University Plymouth Hospitals NHS Trust over a three-year period.

#### **Sample size calculation:**

Sample size test calculation was carried out with the G\*Power 3.1 program (Faul *et al.*, 2007) for comparison of the main outcome measure of dynamic balance (between IOL design) using mixed ANOVA (repeated measures, between factor being the type of IOL).

Based on of the result of dynamic balance measurement in a previous study (Mancini *et al.*, 2011), an estimated medium effect size (0.25) will be used. With a power of 85% and level of significance ( $p$ ) set at 0.05 and effect size of 0.25, 55 participants will be required in each group (Standard non-Toric vs Toric IOLs). Assuming a 20% drop out rate, to secure 55 participants in each group, 70 participants will therefore be recruited in each group. For two groups of participants (Toric versus non-Toric), a total of 140 participants will be recruited.

### **3.4 Primary endpoint/outcome**

Dynamic stability during functional activities which will be assessed by tracing centre of mass and head tilting using wireless motion sensors and eye tracker. The outcome measures of dynamic stability include the angular position, velocity and acceleration of the sensors.

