### iii. TRIAL SUMMARY

Trial Title	Vision and balance changes after bilateral implantation of Toric versus non-Toric intraocular lenses in Cataract patients with astigmatism	
Internal ref. no. (or short title)	Vision and balance changes after bilateral implantation of Toric IOLs	
Clinical Phase	Pre and post operation comparison	
Trial Design	Randomised controlled trial	
Trial Participants	Ambulatory adult aged over 50 years with bilateral cataract patients and astigmatism >1.0D awaiting intraocular lens replacement surgery	
Planned Sample Size	140 participants	
Treatment duration	Up to 12 months after first eye surgery	
Follow up duration	12 months after second eye surgery	
Planned Trial Period	3 years	
	Objectives	Outcome Measures
Primary	
 
• Dynamic balance in functional activities
 
	
 
• Centre of mass and head movement by accelerometer in crossing obstacles, turning and stair walking
 

Secondary	
 
• Eye tracking characteristics
 
• Visual function
 
• Risk of fall
 
• Vision related quality of life
 
	
 
• Area of interest (heatmap) and gaze duration by eye tracking (Tobii pro2) during level ground obstacle crossing and stair walking
 
• Duration of Timed up and go test Visual acuity
 
• IOL rotation
 
• Fall efficacy scale and fear of falling
 
• CAT-PROM 5 questionnaire
 

Investigational Medicinal Product(s)	Monofocal Toric and non-Toric intraocular lens	
Formulation, Dose, Route of Administration	Artificial intraocular lens implantation during cataract correction surgery	

Vision and balance changes after bilateral implantation of Toric IOLs  
IRAS ID: 286913

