### 3.6 Table of endpoints/outcomes

Objectives	Outcome Measures	Timepoint(s) of evaluation of this outcome measure (if applicable)

Primary Objective To compare dynamic stability in cataract patients with Toric versus non-Toric IOLs
	
Dynamic stability: - movement of centre of mass and head tilting using wireless motion sensors.
	
Three timepoints:
 
 
1. pre-operation study visit and
 
2. post-operation study visit (3-6 months after first eye surgery).
 
3. post-operation study visit (3-6 months after second eye surgery).
 

Second Objectives To compare eye tracking characteristics, visual functions, risk of falls and quality of life in cataract patients with Toric versus non-Toric IOLs
	
Eye tracking characteristics: -area of interest by gaze pattern -Gaze duration on area of interest
 
Vision function include visual acuity, IOL rotation by degrees of rotation from intended position and degree rotation from the steepest meridian using special optometry equipment to look at the front of the eye (digital slit lamp and Pentacam)
 
Risk of fall will be measured by fear of falling and fall efficacy scale questionnaires. Vision related quality of life will be measured by CAT-PROM5 questionnaire.
	
Three timepoints:
 
 
1. pre-operation study visit and
 
2. post-operation study visit of first eye at 3-6 months after the surgery
 
3. post-operation study visit of second eye at 3-6 months after the surgery
 

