### 10.3.1 Summary of baseline data and flow of patients

[figure not shown]
Randomization	Sample size calculation with the G* Power 3 program N=140	Randomization list generated in MS Excel at the commencement of the study by the Chief investigator: independent of assessment and intervention	Execution- randomization list will be held by the PI (ophthalmologist at REI) so that they know who is allocated into either the intervention or control groups according to the list.
Outcome measures		Trial description	Outcome recorded
Primary outcomes Dynamic stability	1.Eye gazing characteristics	Gazing duration on obstacles during the obstacle negotiation.  Area of interest and corresponding glazing duration during stair walking	
 
Gazing duration and frequency on obstacles and area of interest.
 
Heat map on area of interest from eye tacking device
 
 
all data will be recorded and saved in file name in the format: participant number-obstacle-trial1/2/3-date.

	2.Movement biomechanics	
-participants perform Timed up and go (TU&G) test involving getting up from chair ,then walking over 3m level ground, turning and walking back to sit down on the chair
 
- participants walk over a 3m level ground with obstacles of different contrast colour to background.
 
- accelerometers of head tilting and change in movement of centre of gravity will be recorded during TU&G test and during crossing over obstacles.
	
 
accelerometers data of change in head tilting and centre of gravity will be recorded
 
Duration in seconds of TU&G test
 
 
all data will be recorded and saved in file name in the format: participant number-obstacle-trial1/2/3-date.

Secondary outcomes	1.Refraction and visual acuity	-standardized protocol for routine visual function test	-vision 20/20, sphere cylinder, axis -DVA, NVA -IOL rotation (for Toric IOL group only)
	2.Questionnaire	Short Fall Efficacy Scale International Fear of Falling Questionnaire CAT-PROM 5 Quality of life Questionnaire	

- A CRF form has been prepared for this study

Vision and balance changes after bilateral implantation of Toric IOLs  
IRAS ID: 286913

**Modified CONSORT flow diagram  
for**

**Vision and balance changes using after bilateral  
implantation of Toric versus non-Toric intraocular lenses in  

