### 10.3.2 Primary outcome analysis- Dynamic stability in three functional activities

The following outcomes will be collected at three time points: before surgery, 3 to 6 months after first and second eye surgery.

Outcome measures	Data collected	Data type/ details	Quantitative Statistical Analysis
Dynamic stability during turning, obstacle crossing and stair walking	Accelerometers data (angular position and acceleration) of change in head tilting and centre of mass will be recorded  Performance of TU&G test	Interval  Centre of mass and head movement will be calculated using ProMove 3D (Inertia Technology, The Netherlands) and MATLAB.  The angular position, velocity and acceleration of the sensors will be tracked on each participant  Duration in seconds of TU&G test	The average reading of the 3 trials in each functional activity will be calculated.  Mixed ANOVA and post-hoc Bonferroni tests will be used to determine the differences between the Toric IOLs group and Monofocal IOLs group before surgery and 6 months after second eye surgery.

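### No single primary variable or success rule is named: dynamic stability covers six or seven measures, each tested at 0.05, and current sections disagree on which outcomes are primary

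*Combined protocol and SAP*

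**What the plan says.** The primary endpoint is described in five places, in different terms:

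- Trial summary: "Centre of mass and head movement by accelerometer in crossing obstacles, turning and stair walking".
- Section 3.4: the endpoint is "assessed by tracing centre of mass and head tilting using wireless motion sensors and eye tracker", and "The outcome measures of dynamic stability include the angular position, velocity and acceleration of the sensors".
- Section 3.6: "movement of centre of mass and head tilting using wireless motion sensors", with no activity named.
- Section 10.3.1: the primary block opens with "1.Eye gazing characteristics". For movement it says "accelerometers of head tilting and change in movement of centre of gravity will be recorded during TU&G test and during crossing over obstacles", and it adds TUG duration.
- Section 10.3.2: "Accelerometers data (angular position and acceleration) of change in head tilting and centre of mass will be recorded". The next column adds velocity and also "Duration in seconds of TU&G test".

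Section 10.3 sets the significance level at 0.05. It specifies a mixed ANOVA with lens type between subjects and time (before or after surgery) within subjects, followed by post-hoc Bonferroni tests. Section 10.3.2 averages three trials per activity and compares the arms before surgery and after second-eye surgery. Section 10.1 takes f = 0.25 from a JERK score in an earlier study and derives 55 per arm for 85% power, or 70 per arm after allowing for dropout.

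**The concern.** The primary objective is tied to a construct, not to a variable. A reader cannot tell which sensor location, quantity, activity or ANOVA term decides whether it has been met. The lead measure, and the standing of gaze and TUG duration, could therefore be settled after the results are seen.

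The sample size was derived for one outcome measure, but the score behind its effect size is not among the outcomes to be analysed. The 85% power therefore belongs to no named endpoint. The trial is meant to inform which patients should be offered Toric lenses, so its confirmatory question needs one pre-specified answer.

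**Working it through.** **1. The plan's sample size.** Section 10.1 gives f = 0.25, level 0.05, N = 110 and power 85%. It does not state the number of measurements m or their correlation ρ. I take m = 2 from the two-level time factor in section 10.3 and assume ρ = 0.5. For the between-arm main effect:

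λ = f²·N·m / (1 + (m−1)ρ) = 0.0625 × 110 × 2 / 1.5 = 9.17, on 1 and 108 df, which gives power 0.851.

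This matches the stated figure. Dropout: 55/0.8 = 68.75, so 69 per arm; the plan rounds up to 70. The number is sound for one variable, one test at 0.05 and that term.

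**2. What the matched test assumes.** With two equal arms, f = 0.25 is a difference of 0.5 SD. The main effect averages the visits before and after surgery, but randomised arms should not differ before a lens is implanted. Suppose the 0.5 SD difference exists only after surgery, with equal SDs and 55 per arm, so √(55/2) = 5.244. The noncentrality is then:

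- main effect: 5.244 × 0.25/√((1+ρ)/2)
- group-by-time interaction: 5.244 × 0.5/√(2(1−ρ))
- baseline-adjusted comparison: 5.244 × 0.5/√(1−ρ²)

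| ρ | Main effect | Interaction | Baseline-adjusted |
|---|---|---|---|
| 0.3 | 1.63, power 36% | 2.22, power 59% | 2.75, power 78% |
| 0.5 | 1.51, power 32% | 2.62, power 74% | 3.03, power 85% |
| 0.7 | 1.42, power 29% | 3.39, power 92% | 3.67, power 95% |

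The choice of deciding term therefore changes the power greatly, and the plan does not make that choice.

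**3. Number of primary measures.** The documents print no count. Two body measures (centre of mass, head) × three activities = 6. Adding TUG duration gives 7. Testing angular position, velocity and acceleration separately would give more, but the plan does not say that it will.

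**4. False-positive chance.** This is conditional on reading any one p<0.05 as success, with no lens effect. Independent tests: 1 − 0.95⁶ = 26.5%; 1 − 0.95⁷ = 30.2%. For equally correlated normal test statistics:

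| Assumed correlation | 0 | 0.3 | 0.5 | 0.7 | 0.9 |
|---|---|---|---|---|---|
| 6 measures | 27% | 24% | 21% | 16% | 11% |
| 7 measures | 30% | 27% | 23% | 18% | 11% |

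**5. Conflicts between current sections.**

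| Item | One reading | Other reading |
|---|---|---|
| Gaze | Primary: 10.3.1 | Secondary: trial summary, 3.5, 3.6, 10.3.3 |
| TUG duration | Primary: 10.3.1, 10.3.2 | Secondary row of the trial summary; absent from 3.5, 3.6 and 10.3.3 |
| TUG summary | Best time: 7.6 | Average of three trials: 10.3.2 |
| Post-surgery time | 6 months: 10.3.2 | 3-6 months: 3.6, 7.7, 7.10 |
| JERK score | Basis of f = 0.25: 10.1 | In no outcome list |

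Section 10.3.2 also gives no axis and no within-trial statistic (such as peak, range or root mean square) for signals that vary throughout a trial.

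**The case against.** The best defence is that the plan is less open than it looks. Sections 3.3 and 10.1 speak of one main outcome measure. Section 10.3.2 fixes averaging over trials and the visits to compare. Bonferroni is specified. Signals from sensors worn on the same body will be correlated, and nowhere does the plan say that one significant result among several is enough.

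Part of this stands. Correlation lowers the error rate, and the any-one-measure rule is only a possible reading. The rest does not answer the point. The one main measure is never identified. Averaging trials does not say what is averaged within a trial. Bonferroni is attached to each mixed ANOVA, so at most it adjusts comparisons within one variable, not across body points, activities or TUG duration.

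Four stronger readings are tempting, but the documents do not support them:

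- **Section 3.4 makes gaze primary.** It names the eye tracker as an instrument, and its next sentence confines the measures to those of the sensors. The real conflict on gaze is section 10.3.1 against the other sections.
- **The activity list is open because section 10.3.1 omits motion recording on stairs.** Stair walking is listed in the trial summary and in sections 3.1, 7.6, 10.3.2 and 16.2, so section 10.3.1 is one incomplete table.
- **The error rate reaches 49-62%.** That needs 13 or 19 independent measures: 2 × 3 × 2 = 12 or 2 × 3 × 3 = 18, plus TUG duration. It adds an assumption of separate tests for each quantity to an unstated success rule.
- **Naming one variable is enough to keep 85% power.** That holds only if the lens difference averages 0.5 SD over both visits, including the one before surgery.

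**Conclusion.** The point holds and should be fixed before any unmasked analysis. That no single primary variable or success rule is named, that the sections conflict and that JERK is in no outcome list all follow from the text without assumptions.

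The false-positive range, about 11-27% for 6 measures and 11-30% for 7 against 5%, illustrates a risk. It rests on derived counts, an assumed correlation between 0.9 and 0, and a success rule that the plan neither states nor excludes. It is not the trial's stated error rate.

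The figure of 110 is not an arithmetic error. It reproduces for one variable under the main-effect test at ρ = 0.5. It is simply not tied to a named endpoint, nor to a test of the difference after surgery.

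**What to change.** Before any unmasked analysis:

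1. Name one primary variable: body point, quantity and axis, within-trial statistic, activity, and how the three trials are combined. Use it in the trial summary and in sections 3.4, 3.6, 10.1, 10.3.1 and 10.3.2.
2. State success as one test at 0.05 of the between-arm difference after second-eye surgery, by the group-by-time interaction or a baseline-adjusted comparison. Do not use the main effect averaged over visits before and after surgery.
3. Reconcile 6 months with 3-6 months, and best with average for TUG duration.
4. Label all other motion measures, TUG duration and gaze as secondary in every table.
5. Justify f = 0.25 for the chosen variable. If JERK is chosen, define it and list it as an outcome. Restate the power for the chosen test with its assumed correlation; the table under step 2 of the working shows the likely range.
6. If more than one activity stays primary, apply Holm across them and restate the power. With three activities, the first step at 0.05/3 takes the 85% reproduced in step 1 down to about 72%.

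The cost is a protocol amendment, a confirmatory claim that rests on one measure, and possibly a less favourable stated power. Recruitment stays at 140.

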### **3.5 Secondary endpoints/outcomes**

1. The eye tracking characteristics (gaze duration, area of interest by gaze pattern and its percentage duration gaze time).

Vision and balance changes after bilateral implantation of Toric IOLs  
IRAS ID: 286913

2. IOL rotation by measuring degrees of rotation from intended position and degrees rotation from steepest meridian with digital slit lamp and IOL tilt and decentration using Pentacam4. This will be part of the routine eye assessment for post cataract surgery with Toric IOL.
3. Visual acuity which is also part of routine eye assessment for all post cataract surgery patients.
4. Fear of falling and fall efficacy scale via questionnaire.
5. Cataract specific quality of life questionnaire (CAT-PROM 5)

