## **8.6 Cataract schedules**

Each eye will be implanted with one IOL in the capsular bag and two separate occasions. PI reported at the time of writing this protocol, the second eye cataract surgery would be scheduled at around four months after the first eye surgery.

Orientation of the IOLs will be checked before and after implantation of IOLs by the ophthalmologists as part of routine care. The PI has extensive experience using Toric IOLs for cataract surgery, they communicated that the cataract surgery using Toric IOLs usually took five to eight more minutes because it took longer time to put in and to ensure the axis of the lenses were in a precise position for correction of astigmatism.

Vision and balance changes after bilateral implantation of Toric IOLs  
 IRAS ID: 286913

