### 10.3.3 Secondary outcome analysis

Outcomes	Data collected	Data type	Quantitative statistical Analysis
Eye glazing characteristics during obstacle crossing and stair walking	Gazing duration on obstacles and area of interest on environment during stair walking  Area of interest determined by heat map (area with highest frequency of gazing)	Interval  Gaze pattern of location of hotspots and duration of gaze will be collected using Tobii pro eye tracker.  % time spent on fixation of highlighted object or area of interest  Best performance among 3 trials will be used.	Mixed ANOVA and post-hoc Bonferroni tests will be used to determine the differences between the Toric IOLs group and Monofocal IOLs group before surgery and 6 months after second eye surgery.
Refraction and visual acuity	-Visual acuity (vision, sphere, Cylinder, Axis, DVA, Add NVA) -IOL tilt and decentration -IOL rotation (for Toric IOL group only)	Interval  Average tilt, decentration and rotation of lens will be analysed by calculating average value in Toric and monofocal groups. Bland Altman will be used to study the agreement of position-level of error for IOLs tilt, decentration and rotation.	Mixed ANOVA and post-hoc Bonferroni tests will be used to determine the differences between the Toric IOLs group and Monofocal IOLs group before surgery and 6 months after second eye surgery.  Unaided and aided distance visual acuity will be recorded in Log MAR and comparisons between the two lenses pre and post cataract surgery will be conducted using a two-way ANOVA. Post-operative refractive astigmatism will be analysed using the Alpins method*. Correlation between SIA and TIA will be assessed, and dependent t-tests will be used to analyse the remaining metrics in the two groups
Questionnaire	Short Fall Efficacy Scale International	Ordinal (non-parametric)	Mixed ANOVA and post-hoc Bonferroni tests will be used to determine the differences between the Toric IOLs group

Vision and balance changes after bilateral implantation of Toric IOLs  
IRAS ID: 286913

	Fear of Falling Questionnaire CAT-PROM 5 Quality of life Questionnaire		and Monofocal IOLs group before surgery and 6 months after second eye surgery.
--	---	--	--

\*Post-operative refractive astigmatism will be analysed using the Alpíns method. Cylindrical power and axis will be converted to vectors (J0 and J45; Equations 1 & 2).

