#### 10.4 Subgroup analyses

Within the Toric IOLs group, a subgroup of participants presented with post-surgery IOL rotation > 5 degree will be isolated to compare the outcomes. This subgroup of participants is very likely to need

Vision and balance changes after bilateral implantation of Toric IOLs  
IRAS ID: 286913

another adjustment surgery. Their data will inform the impact of IOLs rotation on surgery complications and whether such rotation may be related to degree of astigmatism.

In both the Toric IOLs and non-Toric IOLs group, subgroups of different degree of astigmatism: mild (<1.50), moderate (1.5-3.0) and severe (3.0+) will be differentiated to compare the outcomes to help inform if Toric IOLs offer similar beneficial effect across cataract patients with wide range of astigmatism. This will help to identify which patients should be referred for Toric IOLs and support evidence-based practice.

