## 16.2 Appendix 2 - Schedule of Procedures

Procedures	Visits x3					
	Screening	Baseline (study visit 1)	Treatment Phase (routine cataract surgery schedule and care)		Follow Up after 1 st eye surgery (study visit 2)	Follow Up after 2 nd eye surgery (study visit 3)
Informed consent	x	x				
Demographics		x				
Medical history	x	x				
General eye examination		x			x	x
Visual function -visual acuity -astigmatism power	x	x			x	x
Eligibility assessment	x					
Randomisation	x	x				
Dispensing of Toric and Monofocal IOLs		x	x	x		
Compliance (IOLs post-op care)			x	x		
Dynamic stability assessment 1. Motion sensor and eye tracking during Timed up & go test (TUG)		x			x	x
Dynamic stability assessment 2. Motion sensor and eye tracking during walking over obstacles		x			x	x
Dynamic stability assessment 3. Motion sensor and eye tracking during stair walking		x			x	x
Risk of fall Questionnaires -Short Fall Efficacy Scale -Fear of falling		x			x	x
Quality of life questionnaire -CAT-PROM5		x			x	x
IOL orientation (Toric IOL only)		x			x	x

Vision and balance changes after bilateral implantation of Toric IOLs  
IRAS ID: 286913

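### The endpoint called IOL rotation is total misalignment: no end-of-surgery axis is planned as study data, so placement error enters the >5 degree group in section 10.4 to an unknown extent

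*Combined protocol and SAP*

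**What the plan says.** Section 3.5 lists the endpoint as "IOL rotation by measuring degrees of rotation from intended position and degrees rotation from steepest meridian with digital slit lamp". The table in section 3.6 gives the same two references, "by degrees of rotation from intended position and degree rotation from the steepest meridian using special optometry equipment", and times the first post-operative reading as "post-operation study visit of first eye at 3-6 months after the surgery", with a matching visit for the second eye. Neither reference is the position of the lens when surgery ended.

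Section 8.6 says "Orientation of the IOLs will be checked before and after implantation of IOLs by the ophthalmologists as part of routine care". It does not say that an axis in degrees is written down, passed to the study or used as a reference.

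In the schedule of procedures (section 16.2), the row beginning "IOL orientation (Toric IOL only" is marked at study visits 1, 2 and 3. The two treatment-phase columns are empty in that row.

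Section 10.4 says that, within the Toric arm, "a subgroup of participants presented with post-surgery IOL rotation > 5 degree will be isolated to compare the outcomes". It continues: "Their data will inform the impact of IOLs rotation on surgery complications", and it also asks whether rotation is related to the degree of astigmatism. Section 10.3.3 adds "Bland Altman will be used to study the agreement of position-level of error for IOLs tilt, decentration and rotation". Neither section names the reference axis.

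**The concern.** A lens can be off its intended axis at 3-6 months because it was placed off axis, because it moved afterwards, or both. Placement belongs to the operation and later movement belongs to the lens. The protocol itself treats them as different things: section 2.1 describes rotation as something the implanted lens does, while section 8.6 describes setting the axis precisely as a step in surgery.

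A single late reading against the intended axis gives only the sum. If the plan is followed as written, an eye with a misplaced but stable lens is labelled as rotated. Findings on what rotation does, or on whether it goes with higher astigmatism, could then be findings about placement. An end-of-surgery axis that is not recorded at the time may not be recoverable later.

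**Working it through.** **Is there a plan figure to reproduce?** Not for rotation: the documents give no SD, expected count or sample size for it. Section 2.1 says about 1% of patients have significant rotation but gives no threshold in degrees, so it cannot be used to calibrate an SD. The primary-outcome sample size does reproduce: a between-groups F test with f = 0.25, alpha 0.05, two time points and an assumed correlation of 0.5 has noncentrality 0.25² × 110 × 2 / 1.5 = 9.17 and power 0.851 at 55 per group. Nothing below depends on it.

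**Is a starting axis captured?**
- The visit 1 mark cannot supply one. No study lens is implanted, and section 6.2 excludes previous intraocular surgery.
- The treatment-phase columns hold no axis reading.
- The steepest meridian is a property of the cornea, so it is not a starting lens position either.

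**What the planned measure contains.** For one eye,

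visit axis − intended axis = (end-of-surgery axis − intended axis) + (visit axis − end-of-surgery axis),

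that is, misalignment M = placement error E + rotation R.

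**How far this could matter (assumed SDs).** Take E and R as independent, normal, with mean zero and SDs s_E and s_R.

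- Flagged: P(|M|>5) = 2[1 − Φ(5/√(s_E² + s_R²))].
- Truly rotated: P(|R|>5) = 2[1 − Φ(5/s_R)].
- Share of flagged eyes with |R| ≤ 5: integrate (1/s_R)φ(r/s_R) × [1 − Φ((5−r)/s_E) + Φ((−5−r)/s_E)] over r from −5 to 5, and divide by P(|M|>5).

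Example with s_E = s_R = 3: √18 = 4.24 and 5/4.24 = 1.18, so 23.9% are flagged. Truly rotated: 5/3 = 1.67, so 9.6%. Share of flagged eyes with |R| ≤ 5: 74%.

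| s_R | s_E | Truly >5° | Flagged >5° | Flagged eyes with rotation ≤5° |
|---|---|---|---|---|
| 2 | 1 | 1.2% | 2.5% | 65% |
| 2 | 3 | 1.2% | 16.6% | 96% |
| 2 | 5 | 1.2% | 35.3% | 98% |
| 3 | 1 | 9.6% | 11.4% | 33% |
| 3 | 3 | 9.6% | 23.9% | 74% |
| 3 | 5 | 9.6% | 39.1% | 85% |
| 4 | 1 | 21.1% | 22.5% | 19% |
| 4 | 3 | 21.1% | 31.7% | 53% |
| 4 | 5 | 21.1% | 43.5% | 68% |

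Over the same grid (placement SD 1-5, rotation SD 2-4), 14% to 44% of eyes that truly rotated more than 5 degrees are missed because the two errors cancel. As a count, with 55 Toric participants and two eyes each (110 eyes), s_E = s_R = 3 gives 26.2 flagged eyes against 10.5 truly rotated.

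**Reading error in the alternative.** Visit axis minus end-of-surgery axis carries two reading errors, which add 2e² to the variance if each has SD e. For s_R = 2 to 3:
- e = 1: 4% to 13% flagged, of whom 80% to 45% truly rotated 5 degrees or less.
- e = 2: 15% to 23% flagged, of whom 95% to 72% truly rotated 5 degrees or less.

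The planned measure carries one reading error plus placement, s_E² + e². On this model the new measure classifies rotation better only when s_E exceeds e. Whatever the noise, it is free of placement error.

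**The case against.** **The measure is valid for what drives vision.** Section 9.5 says each 3 degrees off axis costs 10% of the correction, so 5 degrees costs 5/3 × 10% = 16.7%, whatever the cause. Section 3.2 names lens orientation as the objective, and the reference axes are stated openly. This stands. Total misalignment is the right quantity for comparing outcomes; the fault lies in calling it rotation and drawing rotation conclusions from it.

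**Replacing the measure in section 10.4 would do harm.** A reader might infer that the >5 degree group should simply be redefined on true rotation. That would move misplaced but stable eyes into the comparison group although their correction is equally reduced. The objection is right, and both quantities are needed.

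**The size is not known.** A reader might infer that the group would consist mostly of placement error. That follows if placement SDs are taken to be at least as large as rotation SDs: placement SD 3-5 with rotation SD 2-3 gives 74-98%. The documents do not support restricting the range in that way; section 8.6 describes extra time spent on a precise axis.

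**The starting axis may not exist as a number.** Section 8.6 says orientation is checked. A recorded value in degrees is a reasonable hope, not a documented fact.

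**Two visits might partly separate the components.** If visit 3 re-reads the first eye, the change since visit 2 is free of placement error. The plan does not say that it does, and movement before visit 2 would still be missed.

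**Conclusion.** The point holds on definition and schedule. As written, the endpoint is total misalignment, no starting axis is planned as study data, and section 10.4 would attribute some placement error to rotation. That placement error enters and enlarges the >5 degree group follows from the algebra, given independent, zero-mean errors. Whether it dominates cannot be settled from the documents: the share of flagged eyes that rotated 5 degrees or less runs from about 19% to 98% over assumed placement SDs of 1-5 and rotation SDs of 2-4 degrees, ignoring reading error.

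Two further readings go beyond the documents. One is that the trial uses this endpoint to judge lens stability: rotational stability appears only in the product description (section 8.3), and the stated uses are those in section 10.4. The other is that the trial's main result is at risk: this is a secondary outcome, and rotation is read in the Toric arm only. The randomised primary comparison and the 140 participants are unaffected. The change is worth making before surgery starts, because the missing value may not be recoverable later.

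**What to change.** 1. In section 16.2, move the visit 1 mark for IOL orientation to the two treatment-phase columns. Record the end-of-surgery axis in degrees, taken from the routine check in section 8.6, on a surgical CRF kept from the masked assessors (section 7.4).
2. In sections 3.5, 3.6 and 10.3.3, define two quantities per eye, each wrapped to ±90 degrees: misalignment (visit axis minus intended axis) and rotation (visit axis minus end-of-surgery axis). Report them separately, and name the reference axis for the Bland-Altman analysis.
3. In section 10.4, use misalignment for the outcome comparison, and rotation for the questions on complications and on degree of astigmatism. State the reference axis each time.
4. If no numeric end-of-surgery axis can be recorded, call the endpoint misalignment and drop the conclusions specific to rotation.

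The cost is one CRF field per operation and a small schedule change, provided the routine check yields a number; otherwise a standardised reading has to be agreed, or item 4 applies. The drawback is that the rotation measure carries two reading errors, so reading precision should be reported with it. Sample size does not change.
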